APPENDIX 2. FAGERSTRÖM TEST OF NICOTINE DEPENDENCE

The Fagerström Test of Nicotine Dependence (FTND) has been shown to be a reliable and valid measure of nicotine dependence¹⁸ and will be administered at the randomization visit only. Copies of this FTND will be provided in the study Procedure Manual. Analysis of results is outlined in the study Statistical Analysis Plan.

Question	Response	
How soon after you wake up do you smoke your first cigarette?	Within 5 minutes	
	6-30 minutes	
	31-60 minutes	
	After 60 minutes	
Do you find it difficult to refrain from smoking in places where it is forbidden (for example in church, at the library, in a cinema, etc.)?	Yes	
	No	
Which cigarette would you hate most to give up?	The first one in the morning	
	All others	
How many cigarettes/day do you smoke?	10 or less	
	11-20	
	21-30	
	31 or more	
Do you smoke more frequently during the first hours after waking than during the rest of the day?	Yes	
	No	
Do you smoke if you are so ill that you are in bed most of the day?	Yes	
	No	

APPENDIX 3. SMOKING SELF-EFFICACY QUESTIONNAIRE (SEQ-12)

The Smoking Self-Efficacy Questionnaire (SEQ-12)¹⁹ is a validated instrument to assess baseline situations in which people might be tempted to smoke and will be administered at the randomization visit only. Copies of this questionnaire will be provided in the study Procedure Manual. Analysis of results is outlined in the study Statistical Analysis Plan.

The following are some situations in which certain people might be tempted to smoke. Please indicate whether you are sure that you could refrain from smoking in each situation using one of the following answers:

	1 = Not at all sure	2 = Not Very Sure	3 = More or less sure	4 = Fairly Sure	5 = Absolutely Sure
1. When I feel nervous	1	2	3	4	5
2. When I feel depressed	1	2	3	4	5
3. When I am angry	1	2	3	4	5
4. When I feel very anxious	1	2	3	4	5
5. When I want to think about a difficult problem	1	2	3	4	5
6. When I feel the urge to smoke	1	2	3	4	5
7. When having a drink with friends	1	2	3	4	5
8. When celebrating something	1	2	3	4	5
9. When drinking beer, wine, or other spirits	1	2	3	4	5
10. When I am with other smokers	1	2	3	4	5
11. After a meal	1	2	3	4	5
12. When having coffee or tea	1	2	3	4	5

APPENDIX 4. SHORT FORM OF THE TOBACCO CRAVING QUESTIONNAIRE

The short form of the Tobacco Craving Questionnaire has been validated as a self-report instrument to measure tobacco craving²⁰ and will be administered to study subjects at randomization and each clinic visit (Days 2, 3, 6, 12, 16, 20, 27, and Weeks 5, 6, 7, and 8). Copies of this questionnaire will be provided in the study Procedure Manual. Analysis of results is outlined in the study Statistical Analysis Plan.

Question	Response							
	Strongly Disagree....Strongly Agree							
Factor 1 (emotionality)								
I would be less irritable now if I could smoke.								
If I were smoking now I could think more clearly.								
I could control things better right now if I could smoke.								
Factor 2 (expectancy)								
I would enjoy a cigarette right now.								
A cigarette would taste good right now.								
Smoking a cigarette would be pleasant.								
Factor 3 (compulsivity)								
If I smoked right now, I would not be able to stop.								
I could not stop myself from smoking if I had some cigarettes here.								
I would not be able to control how much I smoked if I had some cigarettes here.								
Factor 4 (purposefulness)								
If I had a lit cigarette in my hand, I probably would smoke it.								
It would be hard to pass up the chance to smoke.								
I could not easily limit how much I smoked right now.								

APPENDIX 5. HOSPITAL ANXIETY AND DEPRESSION SCALE (HADS)

The HADS questionnaire²¹ has been validated as a self-report instrument to measure levels of anxiety and depression and will be administered to study subjects at Screening Visit #1, at the Day 12, Day 27 (End-of-Treatment visit) and again at Week 8. Copies of this questionnaire will be provided in the study Procedure Manual. Analysis of results is outlined in the study Statistical Analysis Plan.

A	I feel tense or 'wound up':
3	Most of the time
2	A lot of the time
1	From time to time, occasionally
0	Not at all
D	I still enjoy the things I used to enjoy:
0	Definitely as much
1	Not quite so much
2	Only a little
3	Hardly at all
A	I get a sort of frightened feeling as if something awful is about to happen:
3	Very definitely and quite badly
2	Yes, but not too badly
1	A little, but it doesn't worry me
0	Not at all
D	I can laugh and see the funny side of things:
0	As much as I always could
1	Not quite so much now
2	Definitely not so much now
3	Not at all
A	Worrying thoughts go through my mind:
3	A great deal of the time
2	A lot of the time
1	From time to time, but not too often
0	Only occasionally
D	I feel cheerful:
3	Not at all
2	Not often
1	Sometimes
0	Most of the time
A	I can sit at ease and feel relaxed:
0	Definitely
1	Usually
2	Not Often
3	Not at all

D	I feel as if I am slowed down:
3	Nearly all the time
2	Very often
1	Sometimes
0	Not at all
A	I get a sort of frightened feeling like 'butterflies' in the stomach:
0	Not at all
1	Occasionally
2	Quite Often
3	Very Often
D	I have lost interest in my appearance:
3	Definitely
2	I don't take as much care as I should
1	I may not take quite as much care
0	I take just as much care as ever
A	I feel restless as I have to be on the move:
3	Very much indeed
2	Quite a lot
1	Not very much
0	Not at all
D	I look forward with enjoyment to things:
0	As much as I ever did
1	Rather less than I used to
2	Definitely less than I used to
3	Hardly at all
A	I get sudden feelings of panic:
3	Very often indeed
2	Quite often
1	Not very often
0	Not at all
D	I can enjoy a good book or radio or TV program:
0	Often
1	Sometimes
2	Not often
3	Very seldom

*Note: The actual questionnaire will not indicate the category (A=anxiety, D=depression) or the points, which are provided here to show how responses will be scored for analysis.

APPENDIX 6. ALCOHOL USE QUESTIONNAIRE

The following questions will be administered to study subjects at randomization and again at Week 8 upon completing the Follow-up Assessment Period. Copies of this questionnaire will be provided in the study Procedure Manual. Analysis of results is exploratory and outlined in the study Statistical Analysis Plan.

1. Over the past 7 days, how often did you have a drink containing alcohol? Consider a “drink” to be a can or a bottle of beer, a glass of wine, a wine cooler, or one cocktail or a shot of hard liquor (like scotch, gin, or vodka).
 - Never
 - 2 to 3 times
 - 4 to 5 times
 - 6 or more times
 - Don’t know
2. If you did drink in the past 7 days, how many drinks did you have on a typical day when you drank alcohol?
 - 1 to 2 drinks
 - 3 to 4 drinks
 - 5 to 6 drinks
 - 7 to 9 drinks
 - 10 or more drinks
 - Don’t know
3. If you did drink in the past 7 days, how often did you have 6 or more drinks on one occasion?
 - Never
 - Daily or almost daily
 - Don’t know

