6.2. Other Efficacy Objectives

Each of the following will include comparisons for 1.5 mg or 3.0 mg doses versus placebo when given as the commercial 25-day titration schedule and for the tid treatment schedule as well as comparisons between the commercial 25-day titration versus tid treatment schedules).

1. Assess the probability of abstinence from Week 5 to Week 8 post-randomization in subjects randomized to cytisine as compared to subjects randomized to placebo.
2. To compare cytisine and placebo arms on initial quit rates during study treatment, at Week 4 (End of Treatment) and on 7-day point prevalence abstinence at Week 5, Week 6, Week 7, and Week 8.
3. Among subjects abstinent at Week 4, compare time to failure to maintain abstinence through Week 8 between arms.
4. To explore potential relationships between subject-reported outcomes (e.g. anxiety, withdrawal symptoms, depression, tobacco craving, alcohol use) with the reduction in cigarette smoking during the study Treatment Period, as well as smoking cessation outcomes at Week 4 (End of Treatment) and from Week 5 to Week 8 post-randomization.
5. To explore a potential correlation for subject's nicotine metabolite ratio (NMR) with the reduction in cigarette smoking and smoking cessation outcomes.

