10.2.6. Relationship Between Outcome Variables and Smoking Cessation

This objective will explore relationships between subject-reported outcomes and smoking cessation outcomes during the study treatment period (primary efficacy endpoint), as well as smoking cessation endpoints at Week 4 (initial quit rate endpoint) and from Week 5 to Week 8 (abstinence from Week 5 to Week 8 endpoint). It is expected that the relationship between each

of these endpoints and each of the following subject-reported outcome variables will be evaluated for this objective:

- Change during the treatment period, in self-reported number of cigarettes smoked over the previous 24 hours.
- Total scores, and change from baseline scores, for the following questionnaires: HADS, SBQ-R, Tobacco Craving, and Alcohol Use.
- Adverse event outcomes such as whether the subject experienced any adverse events, any serious adverse events.
- Compliance outcomes such as percent of study drug taken, number of behavioral support sessions attended.

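### The alcohol questionnaire has no answer for one drinking occasion in the week or for heavy drinking on only some days, and the SAP asks for an alcohol score that is never defined

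*Protocol*

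**What the plan says.** Protocol Appendix 6 sets out three alcohol items.

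- Item 1 asks "Over the past 7 days, how often did you have a drink containing alcohol". The answers are never, 2 to 3 times, 4 to 5 times, 6 or more times, and don't know.
- Item 2 asks for the number of drinks on a typical drinking day, in bands from 1 to 2 up to 10 or more, plus don't know.
- Item 3 asks "If you did drink in the past 7 days, how often did you have 6 or more drinks on one occasion". The answers are never, "Daily or almost daily", and don't know.

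On timing, the appendix states: "The following questions will be administered to study subjects at randomization and again at Week 8". On status, it states: "Analysis of results is exploratory and outlined in the study Statistical Analysis Plan".

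Alcohol use is one of the examples of subject-reported outcomes in other efficacy objective 4 ("e.g. anxiety, withdrawal symptoms, depression, tobacco craving, alcohol use", Protocol 6.2). These are to be explored against smoking reduction and cessation.

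The SAP uses the form in four places. Section 4.1.2 lists responses to the questionnaire. Section 8.6 tabulates each item response at baseline. Section 10.2.8 summarizes the items categorically by arm and visit. Section 10.2.6 instead lists "Total scores, and change from baseline scores, for the following questionnaires: HADS, SBQ-R, Tobacco Craving, and Alcohol Use" as the variables to be related to the smoking endpoints.

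**The concern.** A closed-answer item works only if every possible true answer has a category. Two of the three items fail that test, and neither document gives a rule for coding a subject who falls in a gap. The same form is used at both visits, so the baseline table, the Week 8 table and any comparison between them are affected.

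The gaps sit where change might be expected. The counseling topics in Protocol Appendix 7 link alcohol with relapse and suggest that subjects consider limiting it. A subject who cuts down to a single occasion, or from near-daily to occasional heavy drinking, cannot report it.

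The SAP wording is a separate problem. A programmer following 10.2.6 would have to invent an alcohol score after the fact, including a value for don't know.

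**Working it through.** There is no planned figure to reproduce. The check lists every possible true answer in the 7-day window and looks for a category that contains it. The answer lists come from Protocol Appendix 6.

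**Item 1, drinking occasions in 7 days**

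| True value | Category offered |
|---|---|
| 0 | never |
| 1 | none |
| 2–3 | 2 to 3 times |
| 4–5 | 4 to 5 times |
| 6 or more | 6 or more times |

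One value, exactly 1, is uncovered.

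**Item 2, drinks on a typical drinking day.** The bands 1–2, 3–4, 5–6, 7–9 and 10 or more leave no gap.

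**Item 3, days with six or more drinks, out of 7**

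| True value | Category offered |
|---|---|
| 0 | never |
| 1–4 | none |
| 5 | none, unless near-daily is read loosely |
| 6–7 | near-daily category |

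The near-daily label is not defined, so where it starts is an assumption. Days 1 to 4 are uncovered on either reading.

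**What change looks like on the form.** Take a subject whose occasions fall from 3 at randomization to 1 at Week 8. The record can show 2 to 3 times at both visits (no change), a move to never (the fall is overstated), or don't know or a blank (missing). None is correct. The same holds for a fall in heavy drinking from 6 days to 2.

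**How many subjects.** On item 1 the number affected at randomization is f × 250, where f is the share who drank exactly once in the week. Each percentage point of f is 0.01 × 250 = 2.5 subjects. Neither document gives f or any drinking distribution, so the product cannot be evaluated. At Week 8 the base is smaller if subjects have left the study.

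**The score.** SAP 8.6 names scores for the SBQ-R, HADS, FTND, SEQ-12 and craving questionnaires. For alcohol it gives only counts and percentages of item responses. Sections 4.1.2 and 10.2.8 also work with responses. Only 10.2.6 asks for a total and a change score, and no rule for adding the three items appears in Appendix 6 or the SAP.

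**The case against.** The strongest case against is that little depends on this form. Appendix 6 calls the analysis exploratory, and objective 4 lists alcohol use last among its examples. SAP 6.5 does not include it among the key endpoints. No primary, abstinence or safety endpoint is derived from it. All of that stands and limits the weight of the point.

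The form that subjects actually complete is also not visible. Copies are in the Procedure Manual and the data are entered in an eCRF, neither of which is available here. A line lost when the PDF was read cannot be fully excluded. Against that, no gap is marked, item 2 in the same appendix is contiguous, and two separate items would each have to have lost lines. This is a reason to check first, not to drop the point.

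Changing the options partway through could give one subject different categories at baseline and Week 8. That objection is sound, and the fix has to allow for it.

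Three stronger readings are tempting, and the documents do not support them.

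- A reader might infer that alcohol use as a whole is misrecorded. Only subjects whose true answer falls in a gap are affected, and some of those will give a missing answer rather than a wrong one.
- A reader might infer that the items can no longer be ordered. The remaining categories, leaving don't know aside, are still ordered; a missing level costs resolution, not order.
- A reader might put a headcount on the problem. Any such figure would rest on an assumed drinking pattern that neither document supplies.

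**Conclusion.** The point holds as a small but definite defect. Followed as printed, item 1 cannot record exactly one drinking occasion, and item 3 cannot record heavy drinking on 1 to 4 days (1 to 5 on the stricter reading of near-daily). Affected subjects give a wrong or missing answer at both visits, and some reductions cannot be seen. How many are affected is unknown.

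The consequence is limited to the alcohol tables and the exploratory alcohol relationships under objective 4. It does not touch the trial's efficacy or safety conclusions. It is still worth correcting because the Protocol synopsis says this trial is meant to test the procedures planned for Phase 3.

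The undefined alcohol score in SAP 10.2.6 is a separate inconsistency that stands whatever the operative form contains. The conclusion on the answer lists assumes that the Procedure Manual and eCRF copies match Appendix 6.

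**What to change.** 1. Compare the Procedure Manual and eCRF copies with Appendix 6. If they already contain the missing options, correct the appendix only.
2. If they match, add a once category to item 1 and intermediate frequencies to item 3 (for example 1 time, 2 to 3 times, 4 or more times, stating how the last relates to the near-daily category). Use the revised form for subjects not yet enrolled and for Phase 3.
3. For subjects already enrolled, keep the same version at randomization and Week 8, and flag the version in the data. State in the SAP that one occasion and intermediate heavy drinking could not be recorded on that version, and that the change tables are limited accordingly.
4. In SAP 10.2.6, remove alcohol use from the list of total and change scores. Relate the item responses to the smoking endpoints, in line with SAP 4.1.2, 8.6 and 10.2.8.

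The cost is a small form and eCRF edit and a short SAP correction. If enrolment has started, there will also be two form versions to keep apart in the tables. If all responses have been collected, only the SAP changes and the Phase 3 form remain to be done.

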APPENDIX 7. BEHAVIORAL SUPPORT

Each participating site must have at least two or more staff members experienced and qualified to provide smoking cessation counseling. Study site counselors who provide behavioral support during this study are required to have either a) a master's level or higher degree in some sort of counseling profession (e.g. health educator, chemical dependence counselor) or b) completed a tobacco treatment training course of at least 4 hours.

At the Screening Visit #2 visit, subjects will be provided behavioral support and assistance in developing a quit plan. Most importantly this ensures the subject's quit date is chosen prior to randomization and that they are planning on trying to quit smoking. Site counselor(s) are to encourage subjects to continue study drug as scheduled even if they lapse and have a cigarette after their quit date. It is important during this "grace" period for the subjects to keep trying to quit as planned. It is also important to reiterate to each subject that the purpose of this study is to evaluate the potential benefits of cytisine in achieving abstinence even after a lapse or "slip" during study treatment because cytisine is thought to block the effects of nicotine.

Subjects will be given the National Cancer Institute, "Clearing the Air" booklet, American Heart Associate "Managing Stress" handout, and the American Thoracic Society, "What is Second and Third Hand Smoking?" handout at the randomization visit.

Subjects will be given a list of 2-3 U.S. websites (e.g. www.smokefree.gov, www.cancer.org/healthy/stay-away-from-tobacco/guide-quit-smoking, www.heart.org/en/healthy-living/healthy-living-lifestyle/quit-smoking-tobacco) as resources.

Subjects will receive up to 12 behavioral support sessions by a qualified staff member, starting at the Screening Visit #2, again at randomization and then continuing through each clinic visit up to the Week 8 visit.

Each behavioral session will be subject-driven and must include direct engagement with the subject about their attempt to quit smoking. Counselors must be warm, empathetic, and genuine so that the subject is comfortable and will share issues and challenges that can be discussed further. In addition, the counselor is to be well-versed on study drug administration and expected side effects of cytisine and able to clearly review and discuss these topics with the study subject. Subjects will be encouraged to "keep trying" if they experience set-backs or a "lapse" during treatment. Each session should last up to 10 minutes.

Practical counseling (problem solving/skills training) should be given. Topics include, but are not limited to, the following:

- Abstinence—Striving for total abstinence is essential. Not even a single puff after the quit date.
- Past quit experience—Identify what helped and what hurt in previous quit attempts. Build on past success.
- Anticipate triggers or challenges in the upcoming attempt—Discuss challenges/triggers and how the subject will successfully overcome them (e.g., avoid triggers, alter routines).

- Alcohol—Because alcohol is associated with relapse, the subject should consider limiting/abstaining from alcohol while quitting. (Note that reducing alcohol intake could precipitate withdrawal in alcohol-dependent persons).
- Other smokers in the household—Quitting is more difficult when there is another smoker in the household. Subjects should encourage housemates to quit with them or to not smoke in their presence.
- Recognize danger situations—Identify events, internal states, or activities that increase the risk of smoking or relapse (i.e. smoking cues and availability of cigarettes, experiencing urges)
- Develop coping skills—Identify and practice coping or problem solving skills. Typically, these skills are intended to cope with danger situations (i.e. learning to avoid temptation and triggers)
- Provide basic information—Provide basic information about smoking and successful quitting.

Worksheets containing questions will be provided and may be administered by the counselor to initiate/foster open conversation with the subject and may be used at the start or during the study. These questions do not need to be used at every visit. They are provided as guidance if the subject has difficulty opening up a discussion.

Potential questions are:

- What is my motivation for quitting?
- Why is it important for me to quit right now?
- What are the biggest barriers I will encounter without a cigarette?
- What are some alternatives I can do when I face these barriers instead of smoking?
- How will I handle withdrawal symptoms?
- What are my stress triggers for cravings?
- How will I deal with these stressors instead of smoking?
- What are my biggest concerns/fears about quitting smoking?
- How will I remember to take my medication as directed?

At the end of each visit, the subject will be reminded of supplementary information for additional support including: study staff contact information, Quitline information ([name]), or additional websites.

Any questions regarding the medication or protocol must be answered by qualified study staff. Documentation of the behavioral support must be captured in the subject's source document.

1. INTRODUCTION

The purpose of this Statistical Analysis Plan (SAP) is to provide a thorough description of statistical methods and presentation of the study data to be used for the analysis of data generated from the clinical trial described in protocol ACH-CYT-09: “A Multicenter, Double-blind, Randomized, Placebo-controlled Phase 2b Trial of Cytisine in Adult Smokers”, Version 2.0 (26-September-2018).

This SAP was prepared by [REDACTED] under the direction of the study sponsor, Achieve Life Sciences Inc. (Achieve). It includes details of data handling procedures and statistical methodology. The final statistical analyses will proceed in accordance with this SAP as approved by both Achieve and [REDACTED]. Any deviation from this SAP will be documented in the final CSR. Any deviations from methods described in the protocol are also detailed and explained in this SAP.

For this study, [REDACTED] is responsible for programming of datasets. [REDACTED] will provide to Achieve the Study Data Tabulation Model (SDTM) as well as Analysis Data Model (ADaM) dataset specifications based on:

- SDTM Model 1.4 and SDTM Implementation Guide (SDTM IG) version 3.2.
- ADaM Model 2.1 and ADaM Implementation Guide (ADaM IG) version 1.1.

In addition to the protocol, the following documents were reviewed in preparation of this SAP:

- Electronic Case Report Form (eCRF) version 2.1, 27-Feb-2019
- eCRF Completion Guidelines version 1.1, 28-Feb-2019
- Data Management Plan version 1.0, 05-Sep-2018
- Study Design Specification version 2.1, 27-Feb-2019

[figure not shown]
